### 5.6 Clinical Laboratory Testing

A blood sample is to be obtained at the time of imaging (drawn prior to  $^{18}\text{F}$ -FES injection) and submitted for hormonal analysis (estradiol and sex hormone binding globulin) by the UW Health clinical laboratory. Results from the UW Health clinical laboratory automatically post to the subjects' medical records.

### 5.7 Risk Assessment

Clinicopathologic-based risk scores will be calculated using the University of Southern California/Van Nuys Prognostic Index (21) and the Memorial Sloan-Kettering Cancer Center Nomogram (22).

Genomic-based risk scores will be calculated using the Oncotype DX DCIS test (25, 26). The risk score (0-100) is generated from expression levels of seven cancer related genes and five reference genes (**Table 3**) determined from a patient's biopsy or surgical specimen (25). Scores are further categorized as low-risk (0-38), intermediate-risk (39-54), and high-risk (55-100). Since utilization of the Oncotype DX DCIS score for clinical care is variable (only 1-5% of DCIS patients locally), we will perform an equivalent "research-based" assay using previously published methods (45). Tissue blocks from the surgical specimen will be identified and used for RNA isolation performed by the UW Translational Research Initiatives in Pathology (TRIP) Lab. The [name] lab will then perform quantitative polymerase chain reaction (qPCR) published by Cronin et al (46) and will follow the algorithm of Solin et al (25) to calculate the genomic-based risk score. Results of this research assay will not be used to guide clinical management. A batched analysis will be performed after all subjects are enrolled for those with sufficient remaining tissue.

**Table 3:** 12 gene panel included in the Oncotype DX DCIS Score

Proliferation Group	Hormone Receptor Group	Other	Reference Group
Ki67	PR	GSTM1	ACTB ( $\beta$ -actin)
STK15			GAPDH
Survivin			RPLP0
CCNB1 (cyclin B1)			GUS
MYBL2			TFRC

### 5.8 Repeatability $^{18}\text{F}$ -FES PET/MRI (Optional)

Up to 5 patients with ER+ DCIS who agree to participate in this optional portion of the study will undergo a second (test-retest)  $^{18}\text{F}$ -FES PET/MRI examination. The test-retest exam cannot be performed the same day but should be completed prior to any therapy or surgical excision. This will not delay any scheduled routine standard of care therapy or procedures for the patient. This optional sub-study will be offered to all patients at the time of consent until we have accrued up to 5 patients with ER+ DCIS.

## 6. REGISTRATION PROCEDURES

Patients must not start protocol procedures prior to registration. Patients must complete the breast PET/MRI study prior to surgical/oncologic intervention for their biopsy-proven breast cancer as part of their routine clinical care.

### 6.1 Patient Recruitment

Potentially eligible patients can be identified by several approaches: study coordinator(s) who have access to the clinical breast MRI schedule and the schedules from other providers that serve this patient population (e.g. surgeons), radiologists who are protocoling clinical breast MRI exams in advance, from patients presented at our weekly multidisciplinary and radiologic-pathologic

concordance conferences, and/or through automatic search results of the electronic medical record provided by the Biomedical Informatics Services delivered to the study investigator(s) and study coordinator(s) via REDCap database. The breast imaging radiologist performing radiologic-pathologic concordance after biopsy can also flag patients as potentially eligible.

Recruitment flyers will also be posted in clinics that serve this patient population. Patients interested in learning more about the research will be required to respond to a research team member(s) noted on the flyer.

Study eligibility will be based on the inclusion and exclusion criteria and will be determined by the breast imaging radiologist(s) and/or study coordinator(s). If a patient is potentially eligible for the study, the study coordinator will contact the patient by phone prior to their scheduled MRI and outline the research protocol to the patient. If the patient is interested in the study, the study coordinator will describe the study in more detail and/or record the subject's preferred contact information and make plans to follow-up with the patient by phone to describe the research protocol in more detail. If they choose, an encrypted version of the consent form will be emailed to them to allow additional time to review the form. If the patient indicates they are interested in proceeding with the study, scheduling for F-FES production with the Radiopharmaceutical Production Facility will be coordinated with the patient's clinical breast MRI appointment.

If the patient is uncertain about participating in the study, they can be offered the contact information of an advocate member of the UWCCC Breast Cancer Research Advisory Network (BCRAN) to use as a resource for general information about participating in clinical research.

The consent process will occur prior to the administration of research procedures. During the COVID-19 pandemic, consent procedures will be conducted by phone, when possible, to minimize face-to-face contact subjects have with the research team. A copy of the consent form will be mailed or emailed to subjects prior to the scheduled consent phone call. If emailed, the consent form will be encrypted. A study team member will call potential subjects at the scheduled time to review the information in the consent form including study procedures, risks associated with participation, alternatives to participation and whom to contact for additional information. Any questions will be addressed during the course of the phone call and subjects will be encouraged to contact the study team with any questions or concerns they might have at any time. Upon completion of the consent process, a copy of the signed consent form will be provided in one of the following ways depending on each subject preferences and capabilities:

- Electronic signature will be provided using DocuSign
- Subject will be asked to scan a copy of the entire consent document and email it back to the study team.
- Subject will be asked to take a photo of the signature page and email a copy to the study team.

- If subjects are unable to provide an electronic copy of the signed consent form, they will be asked to bring a copy of the form to the research visit.

Once institutional requirements are met, remote consenting may continue by obtaining electronic signature using the DocuSign software platform.

## 6.2 Patient Enrollment

Study enrollment will occur when the patient arrives for and consents to the research study. A study team member will meet with the patient, review the research protocol, and answer the potential subject's questions. The information in the consent form, including study procedures, risks associated with participation, alternatives to participation and whom to contact for additional information, will be reviewed. Any questions will be addressed prior to the start of any research procedures and all subjects will be reminded that participation is optional and they can change their mind at any time and still get clinically required testing completed. Those interested in participating will be asked to sign informed consent and HIPAA authorization and the subject will be enrolled in the research study. Subjects will be assigned a unique ID number. Both the MRI screening questionnaire as well as the PET screening questionnaire will be reviewed to confirm eligibility criteria.

## 6.3 Eligibility Verification

The patient must meet all of the eligibility requirements listed in Section 4.0.

## 6.4 Registration Content Requirements

- 6.4.1 Protocol Number
- 6.4.2 Investigator Identification
  - Investigator's name
- 6.4.3 Patient Identification
  - Patient's name
  - Patient's address
  - Patient's Medical Record Number (MRN)
  - Patient demographics
  - Gender
  - Birth date
  - Race
  - Ethnicity
  - Date on study

## 6.5 Criteria for Removal from Study

Enrolled patients will be removed from the study in the following circumstances:

- Subject does not complete the PET/MRI examination per study protocol
- Positive pre-scan pregnancy test
- Subject withdraws consent
- Exclusion criteria are discovered after registration but prior to the PET/MRI examination

## **7. TREATMENT/INTERVENTION PLAN**

This is an observational study and the results of the  $^{18}\text{F}$ -FES PET/MRI will not be used to change patient therapy. The results of the research studies will not be reported by a radiologist, will not be part of the patient's medical record, and will not be available to the patient or their physician. The exception is if the breast MRI component of the breast PET/MRI is used as the patient's clinical examination, then interpretation of the breast MRI and management recommendations will be made based on routine clinical practice. No medications will be administered as part of the study protocol except intravenous injection of a gadolinium-based contrast agent for MRI and  $^{18}\text{F}$ -FES PET tracer required for PET imaging.

### **7.1 Administration Schedule**

For each research breast  $^{18}\text{F}$ -FES PET/MRI examination, patients will receive:

- $^{18}\text{F}$ -FES, 6 mCi (222 MBq)  $\pm$  20%, IV slow infusion over 2 minutes followed by saline flush, once
- Gadolinium intravenous contrast (gadobenate dimeglumine; MultiHance), weight-based dosing (0.1 mmol/kg), IV power-injection at 2 cc/second followed by a 20 cc saline flush, once

### **7.2 Dose Modifications**

There will be no dose modifications for  $^{18}\text{F}$ -FES administration.

### **7.3 Supporting Care Guidelines**

All supportive measures consistent with optimal patient care will be given throughout the study. Any adverse effects, related or non-related to the injection of  $^{18}\text{F}$ -FES, will be treated as clinically indicated with no study-related restrictions.

If there is a contrast reaction or extravasation, these will be managed via UW Health guidelines. A physician is always present to manage contrast reactions and extravasations, should one occur.

To facilitate clearance of  $^{18}\text{F}$ -FES, thus reducing patient radiation dose exposure, patients will be instructed to adequately hydrate prior to and after the radiopharmaceutical administration unless on a fluid restrictive diet by their treating physician.

### **7.4 Duration of Follow-up**

Adverse events occurring within 24 hours after  $^{18}\text{F}$ -FES infusion will be recorded by the study coordinator who will contact the subject within 1 to 3 days after  $^{18}\text{F}$ -FES administration. Standard of care patient management will occur after the  $^{18}\text{F}$ -FES breast PET/MRI examination. These visits generally include consultation with a surgeon, radiation oncologist, and/or medical oncologist. Subject's medical records are followed until completion of definitive treatment.

## 8. ADVERSE EVENT REPORTING REQUIREMENTS

### 8.1 Purpose

Adverse event (AE) data collection and reporting, which are required as part of every clinical trial, are done to ensure the safety of the patients enrolled, as well as those who will enroll in future studies using similar agents.

### 8.2 Terminology

- **Adverse Event (AE):** Any untoward medical occurrence associated with the use of a drug in humans, whether or not considered drug related. Therefore, an AE can be **ANY** unfavorable and unintended sign (including an abnormal laboratory finding), symptom, or disease temporally associated with the use of a medicinal product, whether or not considered related to the medicinal product.
- **Attribution:** An assessment of the relationship between the adverse event and the protocol treatment, using the following categories.

ATTRIBUTION	DESCRIPTION
Unrelated	The AE is clearly NOT related to treatment.
Unlikely	The AE is doubtfully related to treatment.
Possible	The AE may be related to treatment.
Probable	The AE is likely related to treatment.
Definite	The AE is clearly related to treatment.

- **CAEPR (Comprehensive Adverse Events and Potential Risks List):** An NCI generated list of reported and/or potential AEs associated with an agent currently under an NCI IND. Information contained in the CAEPR is compiled from the Investigator's Brochure, the Package Insert, as well as company safety reports.
- **CTCAE:** The NCI Common Terminology Criteria for Adverse Events provides a descriptive terminology that is to be utilized for AE reporting. A grade (severity) is provided for each AE term.
- **Hospitalization (or prolongation of hospitalization):** For AE reporting purposes, a hospitalization is defined as an inpatient hospital stay equal to or greater than 24 hours.
- **Life Threatening Adverse Event:** Any AE that places the subject at immediate risk of death from the AE as it occurred.
- **Serious Adverse Event (SAE):** Any adverse event occurring at any dose that results in **ANY** of the following outcomes:
  - Death
  - A life-threatening adverse event

- Inpatient hospitalization or prolongation of existing hospitalization (for  $\geq$  24 hours).
- A persistent or significant incapacity or substantial disruption of the ability to conduct normal life functions.
- A congenital anomaly/birth defect.
- Important Medical Events (IME) that may not result in death, be life threatening, or require hospitalization may be considered a serious when, based upon medical judgment, they may jeopardize the patient or subject and may require medical or surgical intervention to prevent one of the outcomes listed in this definition.

### 8.3 Reporting Procedure

Per 21CFR312.32(c), all adverse events deemed both serious and unexpected associated with the use of the drug must be reported to the FDA and to all participating investigators as soon as possible and in no event later than 15 days.

The FDA will be notified of any unexpected fatal or life threatening experience associated with the drug as soon as possible but in no event later than 7 calendar days. The University of Wisconsin Health Sciences-IRB will be notified in accordance with posted institutional policy.

Serious and Non-Serious Adverse events will be recorded, regardless of whether or not they are thought to be related to the investigational imaging tracer. While all adverse events will be tabulated and reported in the study final report, serious adverse events will be reported in the course of the trial. Adverse events that meet criteria of a serious adverse event listed above will also be recorded and reported.

The Investigator will inform the IRB of all adverse events attributed to the investigational imaging tracer in accordance with posted institutional policy.

### 8.4 Additional Adverse Event Information

**CTCAE term (AE description) and grade:** The descriptions and grading scales found in the revised NCI Common Terminology Criteria for Adverse Events (CTCAE) version 5.0 will be utilized for AE reporting. All appropriate treatment areas should have access to a copy of the CTCAE version 5.0. A copy of the CTCAE version 5.0 can be downloaded from the CTEP web site

[http://ctep.cancer.gov/protocolDevelopment/electronic\\_applications/ctc.htm](http://ctep.cancer.gov/protocolDevelopment/electronic_applications/ctc.htm)

The following adverse event information was obtained from the NCI.

## Condensed risk list – $^{18}\text{F}$ -FES PET

POSSIBLE, SOME MAY BE SERIOUS

• Swelling and redness at the site of the medication injection

• Changes in taste

The only adverse events that have been attributed to PET imaging with diagnostic  $^{18}\text{F}$ -FES at the levels described in the Investigators Brochure have been mild transient disturbances in taste. Therefore, no significant adverse events are expected as a result of the intravenous (IV) administration of  $^{18}\text{F}$ -FES for typical PET imaging applications.

As with any IV administered agent,  $^{18}\text{F}$ -FES could cause an allergic reaction that could potentially pose a threat to life (anaphylaxis). This has not been observed in reported human exposure to date. Reasonable precautions should be taken, consistent with normal radiologic and clinical facility practice. The patient should be monitored until the PET procedure is completed, and trained personnel and emergency equipment should be available per facility standards.

For purposes of informed consent regarding reasonably foreseeable risks to subjects in trials utilizing  $^{18}\text{F}$ -FES, the following potential adverse events are considered extremely rare:

- Injection-related risks that may include infection, or accidental extravasation of the dose that may lead to discomfort, localized pain, or infection.
- Risks related to allergic reaction/anaphylaxis that may be life threatening.

As with all PET imaging agents,  $^{18}\text{F}$ -FES is a radiopharmaceutical that decays with positron emission. As such, it poses an intrinsic radiation exposure risk. However, when administered in accordance with the Investigator's Brochure as a PET imaging agent, this risk is felt to be extremely small. The organ and total body doses associated with  $^{18}\text{F}$ -FES PET imaging are comparable to or lower than those associated with other widely used clinical nuclear medicine procedures.

$^{18}\text{F}$ -FES in combination with other agents could cause an exacerbation of any adverse event currently known to be caused by the other agent, or the combination may result in events never previously associated with either agent.

## 9. MEASUREMENT OF TREATMENT OR INTERVENTION EFFECT

Not applicable since the research imaging study (PET/MRI) will not be used to guide therapy.

## 10. STUDY PARAMETERS

Information regarding time intervals for performance of the study and contact points is included as **Table 2** in Section 5.3.

## 11. DRUG FORMULATION AND PROCUREMENT

### 11.1 Gadolinium-based intravenous contrast agent

Gadobenate dimuglumine (MultiHance) is the gadolinium-based intravenous contrast agent used for the MRI portion of this study. It will be obtained from a commercial source (e.g. Bracco Diagnostics, Inc). This agent is used routinely in standard clinical practice at our institution. Please refer to package insert for more comprehensive information.

### 11.2 16 $\alpha$ -[F]-fluoro-17 $\beta$ -estradiol (F-FES)

F-FES is the radiopharmaceutical which will be used for this study. For complete information, please refer to the Investigator's Brochure: "[F]Fluoroestradiol: An investigational positron emission tomography (PET) radiopharmaceutical for injection, intended for use as an in vivo diagnostic for imaging estrogen receptors in tumors (NCI-held IND 79,005)", Edition Number 4, Edition date 2011.

#### 11.2.1 Other Names

[F-18]FES, FES

#### 11.2.2 Classification

Investigational new drug: Radiopharmaceutical/radiotracer

In May 2020, F-FES was approved by the FDA under the brand name "CERIANNA", but the labelled indication for clinical use is for a different breast cancer patient population (recurrent or metastatic) than included in this research study (DCIS). Thus, we will continue to perform this research study under our existing approved IND.

#### 11.2.3 Mode of Action

F-FES binds to ER alpha with a binding affinity nearly identical to estradiol. F-FES binding to sex steroid binding protein (SBP or SHBG) is also similar to that of estradiol, providing equivalent transport to sites of ER expression, including tumor sites. In breast cancer, the uptake of F-FES, measured by whole body PET/CT, has been shown to correlate with ER expression in biopsy material assayed by *in vitro* radioligand binding or by IHC.

#### 11.2.4 Storage and Stability

In accordance with regulations, the Radiopharmaceutical Production Facility conducts several quality control tests on the F-FES product prior to release for human administration. Once delivered, doses will be stored in the appropriate storage area in the nuclear medicine facility until they are administered to the patient. The drug solution is stored at room temperature in a gray butyl septum sealed, sterile, pyrogen-free glass vial with an expiration time of 6 hours.

#### 11.2.5 Dose Specifics

The injected dose of F-FES will be 6 mCi (222 MBq)  $\pm$  20% with a specific activity greater than 170 Ci/mmol at the time of injection for an activity dose of 6 mCi. In all cases, less than 5  $\mu$ g of F-FES should be injected. F-FES is the only active ingredient. There is no evidence that nonradioactive and radioactive FES molecules display different biochemical behavior.

#### 11.2.6 Preparation

Fluorine-18 labeled FES is synthesized with high specific activity so the quantity of estrogenic material injected with the radiopharmaceutical is  $\leq$  5  $\mu$ g ( $\leq$  17 nmol). For a 6 mCi dose, this would be 170 Ci/mmol. Between 3 and 6 mCi of [F]FES is administered in a nominal volume of 10 mL of phosphate buffered saline containing less than 15% ethanol (v:v) for a single PET scan.

Specific manufacturing processes will follow our approved Drug Master File for F-FES. Briefly, [F]FES is purified by HPLC using an eluent of 50% ethanol, USP in sterile water for injection. The final product [F]FES with a total volume of 10 mL is formulated in 10% ethanol for injection, USP and 0.075M saline for injection, USP, buffered with 0.075M sodium phosphates injection, USP. The concentration of ethanol in the final injectate is less than 15% by volume, or a maximum of 1.5 mL of ethanol. This is less than one-sixth of the amount of ethanol in one alcoholic drink and < 0.025 mL/kg (< 0.02g/kg) for a standard 56.8-kg woman.

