### 5.5.3 $^{18}\text{F}$ -FES Administration

The patient will have an intravenous line placed, typically in the hand or arm opposite to the known primary breast cancer,  $^{18}\text{F}$ -FES will be given by 2-minute infusion, and the dose administered will be approximately 6 mCi  $\pm$  20%. The injection site will be inspected by the technologist to assess for any possible infiltration. The patient will wait approximately 60 minutes to allow for biodistribution and tumor uptake of the radiopharmaceutical prior to imaging. The patient should void prior to image acquisition.

All adverse events occurring within a 24-hour period post-infusion will be recorded (a phone call to the participant performed 1 to 3 days after  $^{18}\text{F}$ -FES infusion is acceptable means of collecting this information). The adverse events to be specifically monitored during the infusion include localized discomfort at the IV injection site, pain, respiratory difficulties, flushing, dizziness, pruritus/rash, and any other symptoms that could be

secondary to an anaphylactic reaction. The subject will be instructed to report any subjective symptoms or sensory changes noted.

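### The 5 µg (17 nmol) mass cap at 6 mCi corresponds to about 353 Ci/mmol, not the stated 170 Ci/mmol, so the specific-activity floor does not secure the cap

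*Combined protocol and SAP*

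**What the plan says.** Three sections of the combined protocol and SAP bear on this.

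- **Section 11.2.6 (Preparation)** gives the reason for high specific activity: "Fluorine-18 labeled FES is synthesized with high specific activity so the quantity of estrogenic material injected with the radiopharmaceutical is" at most 5 µg (at most 17 nmol). The next sentence converts that limit: "For a 6 mCi dose, this would be 170 Ci/mmol". The section then describes the activity given per scan as "Between 3 and 6 mCi of" tracer.
- **Section 11.2.5 (Dose Specifics)** makes the same number a requirement: "specific activity greater than 170 Ci/mmol at the time of injection for an activity dose of 6 mCi". It adds a separate mass limit: "In all cases, less than 5" µg is to be injected.
- **Sections 5.5.3, 7.1 and 11.2.5** give the planned activity as 6 mCi ±20%. In 5.5.3 the wording is "the dose administered will be approximately 6 mCi", with the same tolerance.

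**The concern.** Specific activity is activity divided by amount of substance. Once the activity (6 mCi) and the maximum amount (17 nmol) are fixed, the minimum specific activity follows, and 170 Ci/mmol does not follow from those two numbers.

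This goes beyond a slip in background text, because 11.2.5 uses the figure as a threshold at the time of injection. Section 11.2.6 presents 170 Ci/mmol as the equivalent of the mass cap. A reader who accepts that would think that meeting the floor means meeting the cap. At 6 mCi it does not: a dose could satisfy the floor and exceed the limit on estrogenic material about twofold, and only a separate check of mass would show it.

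**Working it through.** **Inputs, all from the protocol**

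- Mass cap: 5 µg, 17 nmol (11.2.6). The two agree with each other and imply 5 µg / 17 nmol = 294 g/mol.
- Activity: 6 mCi ±20% (5.5.3, 7.1, 11.2.5), so 6 × 0.8 = 4.8 mCi to 6 × 1.2 = 7.2 mCi.
- Stated specific activity: 170 Ci/mmol (11.2.5, 11.2.6).

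**Step 1. Try to reproduce 170 Ci/mmol.** Minimum specific activity = activity / maximum amount.

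| Activity | Calculation with 17 nmol | Minimum specific activity |
|---|---|---|
| 3 mCi | 3×10⁻³ Ci / 17×10⁻⁶ mmol | 176.5 Ci/mmol |
| 4.8 mCi | 4.8×10⁻³ / 17×10⁻⁶ | 282.4 Ci/mmol |
| 6 mCi | 6×10⁻³ / 17×10⁻⁶ | 352.9 Ci/mmol |
| 7.2 mCi | 7.2×10⁻³ / 17×10⁻⁶ | 423.5 Ci/mmol |

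The figure is not reproduced at 6 mCi or anywhere in the permitted range. The ratio at 6 mCi is 352.9 / 170 = 2.08.

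**Step 2. Look for an innocent explanation.**

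- *Rounding of 17 nmol.* 6×10⁻³ / 17.5×10⁻⁶ = 342.9 and 6×10⁻³ / 16.5×10⁻⁶ = 363.6, so the range is 343 to 364 Ci/mmol.
- *Molar mass.* Converting 5 µg with assumed molar masses of 288 to 294 g/mol gives 17.3 to 17.0 nmol, hence 346 to 353 Ci/mmol.
- *Decay after synthesis.* Section 11.2.5 fixes the figure at the time of injection, so decay before injection is already accounted for.
- *Text extraction.* The value 170 appears in both sections, and 5 µg and 17 nmol are mutually consistent, so a corrupted character is unlikely.

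The nearest match is a 3 mCi dose (176.5 Ci/mmol). The figure may have been carried over from that lower activity, but the protocol does not say so.

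**Step 3. What the floor allows if read alone.** Amount = activity / 170 Ci/mmol; mass = amount × 294 g/mol.

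| Activity | Amount at 170 Ci/mmol | Mass |
|---|---|---|
| 4.8 mCi | 28.2 nmol | 8.3 µg |
| 6 mCi | 35.3 nmol | 10.4 µg |
| 7.2 mCi | 42.4 nmol | 12.5 µg |

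The floor matches the cap at 170 × 17×10⁻⁶ = 2.89×10⁻³ Ci, that is 2.89 mCi. This is below the lowest permitted activity of 4.8 mCi, so at no permitted dose does meeting the floor guarantee the cap.

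**Step 4. The activity range in 11.2.6.** Its range of 3 to 6 mCi differs from 4.8 to 7.2 mCi at both ends. This is a secondary, editorial point.

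**The case against.** The strongest reply is that the operative limit is correct and stands on its own. Section 11.2.5 imposes two cumulative conditions: specific activity above 170 Ci/mmol, and mass below 5 µg in every case. A 6 mCi dose at 171 Ci/mmol meets the first and fails the second, so the protocol forbids it. On this view the floor is merely slack, and the one demonstrable error is the conversion sentence in 11.2.6. No section tells anyone to release a dose on specific activity alone. Section 11.2.4 requires quality-control tests before release, and 11.2.6 says manufacture follows an approved Drug Master File, which may hold a correct specification. Section 11.3 also allows a commercial product, which these preparation details do not describe.

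Much of this stands. The 10.4 µg dose is not authorised, and harm to any patient is not shown. The protocol gives no batch specific activities, so it is unknown whether any batch falls between 170 and 353 Ci/mmol. On the other hand, 11.2.4 does not name a mass test, so harm is not excluded either.

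The reply does not make the number right. Section 11.2.6 explicitly presents 170 Ci/mmol as the equivalent of the cap, and 11.2.5 repeats it as a requirement for the same 6 mCi dose. A threshold that fails to do what the text says it does should not rest on a second limit to neutralise it.

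The objection is also fair on the remedy: a single floor of 424 Ci/mmol would be stricter than the cap requires at lower activities, and any correct floor only restates the cap. That favours deletion as the simpler option.

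**Conclusion.** The concern holds. The specific activity that corresponds to 17 nmol at 6 mCi is about 353 Ci/mmol (343 to 364 allowing for rounding of 17 nmol). The protocol's 170 Ci/mmol is too low by a factor of 2.08. As a floor in 11.2.5 it does not secure the 5 µg cap at any permitted activity.

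The result rests only on figures printed in the protocol and on reading the conversion sentence in 11.2.6 as referring to the cap stated just before it, which is the natural reading. It should be fixed because it is a numerical dose specification for an injected agent. Its reach is limited: the separate mass limit still binds, no effect on SUVmax is claimed, and endpoint, sample size, power and analysis are unchanged.

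**What to change.** In 11.2.5 and 11.2.6, do one of the following:

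1. Delete the specific-activity figure and rely on the 5 µg (17 nmol) cap. This is the simplest choice and sufficient by itself.
2. Replace 170 with about 353 Ci/mmol for 6 mCi. If one figure is to cover the whole permitted range, about 424 Ci/mmol is needed for 7.2 mCi.

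Check the chosen wording against the release specification in the Drug Master File before adopting it; whether a higher floor would affect production cannot be judged from the protocol. In 11.2.6, change the activity range to 6 mCi ±20% (4.8 to 7.2 mCi). Recording the injected mass for each scan would be useful but is optional.

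The cost is a text correction in two sections and one document check. No extra patients, procedures or required data fields are needed.
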